5.4 Dose Modification

Dose modifications will not be allowed on this study. Because study agent is only available in a single dose capsule, no dose modification option is available. If a subject is experiencing adverse events or is having a medical procedure that requires a brief **suspension** of letrozole, this must be noted in the CRF on the dose suspension page. At the discretion of the

PI, subjects may be removed from participation for significant dose suspension time periods.

Subjects with grade 2 adverse events considered to be related to study agent will have the agent suspended until the toxicity has resolved. The agent will then be resumed. If toxicity again occurs, and is thought to be agent-related, the agent will be permanently stopped. Grade 2 hot flashes or menstrual irregularities will not be cause for suspending study agent.

Subjects who experience grade 3-4 toxicity will have the study agent suspended. If the investigator is certain that the toxicity is not due to the agent, the agent may be re-instituted after resolution of the adverse event, providing:

- 1) the subject will have had a minimum of three months of study agent prior to biomarker assessment at six or twelve months;
- 2) the investigator feels relatively certain taking letrozole or participating in the study will not affect recovery from the condition

5.5 Interruption or Discontinuation of Treatment

A genuine effort must be made to determine the reason(s) why a subject fails to return for the necessary visits or is discontinued from the trial. Information regarding the reason for not completing the trial will be recorded on the appropriate case report forms.

It will be documented whether or not each subject completed the clinical study. If for any subject study treatment or observations were discontinued the reason will be recorded on the appropriate case report form. Reasons that a subject may discontinue participation in a clinical study are considered to constitute one of the following:

- adverse event(s)
- abnormal laboratory value(s)
- abnormal test procedure result(s)
- subject develops breast cancer
- protocol violation
- subject withdrew consent
- lost to follow-up
- administrative problems
- physician decision
- death

All subjects that discontinue trial prematurely require notification of the Protocol Chair or her designee at KUMC within 72 hours of known discontinuation.

Any subject who receives at least one dose of study agent will be included in the safety analysis.

5.6 Emergency procedure for unblinding

Any adverse event or situation that requires immediate unblinding is subject to the mutual consideration of the Protocol Chair and the Trial Statistician.

5.7 Adherence/Compliance

Each subject will be given a seven month supply of drug/placebo at trial entry and instructed to return all excess drug/placebo to investigator at the six month visit. Six months of dosing is the expected amount of dosing, however, seven months of drug/placebo will be given to each subject to accommodate scheduling issues. At the end of treatment the actual quantity of unused drug/placebo will be compared to the anticipated amount of unused drug. At the six month visit, all subjects have the option to receive seven months of open label drug supply, expected to cover six months of dosing and allow some flexibility with scheduling the repeat RPFNA while on study drug.

Subjects that maintain 70% of study agent intake as measured through patient reports and tablet counts conducted by the trial coordinator will be considered “compliant”. Percent intake will be computed as the number of tablets taken divided by the number of days subject should have taken capsules. Pill counts and compliance will be considered separately for the first six and the last six months in the analysis.

5.8 Drug Records

Drug records regarding receipt, distribution and disposition of study drug will be maintained by the institutional investigational pharmacist. The packing slip will indicate from and to whom study drug/placebo was shipped, date, quantity, and batch or lot number. The dispensing record will indicate quantity and dates that study drug was dispensed to and return by each subject. At the completion of the study, all unused study drug/placebo will either be returned to Novartis or destroyed per Novartis instructions. The record documenting study drug return will include date, quantity, batch or code number, and the name of person/department to whom the drug was returned.

6.0 LETROZOLE INFORMATION

6.1 Letrozole IND Sponsor

Letrozole is an approved agent for treatment of breast cancer and will shortly begin evaluation in The NSABP4 trial as an agent for the primary prevention of breast cancer in postmenopausal women not on hormone replacement therapy. Since in this instance letrozole is being used in an experimental manner, we will file for an IND exemption, as we did for the pilot study.

6.2 Mechanism of Action

Letrozole is a non-steroidal aromatase inhibitor (4, 4'-1H-1,2,4-Triazol-1 ymethylene dibenzonitrile) with a molecular weight of 285.31. It is supplied by Novartis in 2.5 mg tablets for oral administration.

6.3 Pharmacokinetics

Letrozole is rapidly absorbed from the GI tract, and absorption is not affected by food. Letrozole is slowly metabolized to an inactive metabolite whose glucouride metabolite is renally excreted. About 90% of letrozole is recovered in urine. Plasma concentrations at steady state are 1.5 - 2 times higher than after a single dose, but after steady state is reached there is no accumulation over time. Letrozole is weakly protein bound and has a large volume of distribution. No change in letrozole pharmacokinetic parameters have been noted with age or moderate renal impairment. Subjects with moderate hepatic dysfunction had 37% higher mean AUC levels than those without impaired function.

6.4 Pharmacodynamics

Letrozole inhibits aromatase by competitively binding to the heme moiety of cytochrome p450 resulting in a reduction of estradiol and estrone synthesis in all tissues.

In premenopausal animals, letrozole decreases ovarian steroidogenesis, reduces uterine weight, increases LH but not FSH, results in regression of estrogen dependent tumors but does not alter adrenal mineral corticoid or glucocorticoid synthesis.

In postmenopausal women letrozole suppresses conversion of testosterone to estradiol and androstenedione to estrone in the fat, adrenal glands and other tissues. Treatment of postmenopausal women reduces serum estrone, estradiol and estrone sulfate but does not alter adrenal corticosteroid, aldosterone, or thyroid hormone synthesis.

6.5 Drug/Drug Interactions

No drug/drug interactions have been noted with warfarin or cimetidine. Concomitant use of tamoxifen and letrozole may decrease letrozole levels.

6.6. Clinical Indications

Letrozole is currently approved as first and second line therapy of metastatic breast cancer, and for use in the adjuvant setting instead of tamoxifen or after 5 years of tamoxifen in a dose of 2.5 mg per day. In the adjuvant setting, letrozole is given for 5 years

6.7 Adverse Reactions

6.7.1 Compared to placebo in adjuvant setting

Adverse events which occurred more significantly more frequently in the MA.17 trial of extended adjuvant letrozole versus placebo following 5 years of tamoxifen were: hot flashes (net difference + 4%), loss of appetite (net difference + 2%), myalgias (net difference + 3%), arthralgias (net difference + 4%), alopecia (net difference +2%) [Goss 2003].

6.7.2 Compared to tamoxifen in adjuvant setting

In adjuvant trials women randomized to aromatase inhibitors had fewer events, uterine cancers and thromboembolic phenomena compared to tamoxifen [Coombes 2004; Thurlimann 2005; Howell 2005]. However, women randomized to an AI had a similar incidence of hotflashes and a higher incidence of arthralgias, bone mineral density loss, vaginal dryness, pain with intercourse, and loss of libido compared to those taking tamoxifen [Coombes 2004; Thurlimann 2005; Fallowfield 2004; Howell 2005].

6.7.3 Compared to tamoxifen in metastatic setting

In a study of 455 women with metastatic breast cancer with a median exposure time of 11 months the incidence of adverse experiences was similar for Femara (letrozole) (n=455) and tamoxifen (n=455). The most frequent adverse events were nausea (15%), hot flushes (18%), fatigue (11%), dyspnea (14%) and arthralgias (14%). Constipation was noted in 9%, headache 8%, diarrhea in 7%, vomiting in 7%, decreased appetite 4%, weight decrease in 6%, alopecia 5%, lower limb edema in 5%, and hypertension 5% (package insert). Discontinuation of drug for adverse experiences was performed for 2% of patients taking Femara (letrozole) and 3% of those taking tamoxifen. A similar distribution of adverse events has been reported for subjects randomized to letrozole vs placebo in the MA17 trial

6.8 Availability

Both letrozole and matched placebo are to be provided by Novartis to the investigational pharmacy at each participating Institution.

Both letrozole and letrozole placebo supplied in bottles of 100 tablets.

6.9 Agent Distribution

Agent will only be released after documentation of IRB approval of the KUMC-approved protocol and consent.

200 tablets will be dispensed at entry of the subject onto the study so as to provide an adequate number of capsules for 7 months. The 7 months is based on the planned 6 months of administration, plus approximately one additional month if required for scheduling of procedures or travel.

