4.3 Inclusion Criteria for Study Entry

- RPFNA hyperplasia +/- atypia (Masood score of ≥ 13), Ki-67 $\geq 1.5\%$ positivity (≥ 500 cells), extra cells for qRTPCR studies (estimated by lab technician from remaining amount in Preservcyt Container).
- Willing to continue the type, dose and route of their hormonal regimen at baseline aspiration throughout the duration of the study participation (6 months for randomization portion, 12 months if participates in the optional open label period);
- Have reasonable normal organ function before being dispensed study agent/placebo, as defined as:

Platelets	>100,000/dL
Hb	>10 g/dl
Absolute granulocyte count	>1000/uI
Creatinine	<1.5 mg/dl
Albumin	>3.0 g/dl
Bilirubin	<2.0 mg/dl
AST	<2 times upper limit of normal
Alkaline Phosphatase	<2 times upper limit of normal
- Have serum level of 25-OH vitamin D of at least 30 ng/ml prior to study entry.
- Willing to have a repeat RPFNA and mammogram at 6 months and 12 months (if participates in the open label portion of the study) following initiation of study drug.
- Willing to undergo a history, breast and physical exam prior to randomization/starting study agent and at 6 months and be contacted monthly by the trial coordinator during the 6 month study period (12 months if participates in the open label portion of the study);
- Willing to have approximately six tubes of blood drawn at baseline and six months (12 months if participates in open label portion of the study);
- Willing to sign and able to understand separate consents for the RPFNA's and study participation;

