5.1 Dose Regimen and Dose Groups

Letrozole 2.5 mg or letrozole placebo will be given to all trial participants for the first 7 months and open label letrozole the second 6 months. All subjects will be given eight months (one month of overage) of drug at the baseline and 6 months visit to allow for scheduling study procedures. All subjects should have off-study procedures no later than within 36 hours of the last dose of letrozole or placebo. However, if a participant stops study drug prematurely in a unscheduled situation, she should come in for biomarker re-assessment as early as possible.

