5.2 Study Agent Administration

The Institutional Investigational Pharmacy will be responsible for receiving, inventory and dispensing of study agent.

A study number will be assigned to each participant and provided to the investigational pharmacy. Study agent will be dispensed with the study number of each subject. Seven months of study agent will be dispensed. The study coordinator will then give the study agent to the subject with instructions to take one capsule at approximately the same time of day in conjunction with intake of food and at least eight ounces of water and to keep track of missed doses or lost capsules.

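### Section 6.9 calls 200 tablets adequate for 7 months, but at one a day they last 200 days against 212-215, and section 5.1 states a different supply from the other sections (minor)

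*Combined protocol and SAP*

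**What the plan says.** **Tablet count.** Section 6.9 (Agent Distribution): "200 tablets will be dispensed at entry of the subject onto the study so as to provide an adequate number of capsules for 7 months". It explains the seven months as six planned months plus roughly one more for scheduling or travel. Section 6.8 gives bottles of 100, so 200 tablets is exactly two bottles.

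**Dosing rate.** Section 5.2 tells each woman to "take one capsule at approximately the same time of day". Section 3.0 gives 2.5 mg daily and section 6.2 gives 2.5 mg tablets, so one tablet is one day.

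**Length of supply.**
- Section 5.2: "Seven months of study agent will be dispensed".
- Section 5.7: "Each subject will be given a seven month supply of drug/placebo at trial entry", with six months of dosing expected. It offers seven months again for open label.
- Section 7.5: a seven-month supply for open label.
- Section 5.1: "All subjects will be given eight months (one month of overage) of drug", at both the baseline and the 6-month visit. The same section has blinded agent given "for the first 7 months and open label letrozole the second 6 months".

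**Timing of the 6-month sample.** Section 7.5 lets agent continue for as much as a further month, until the RPFNA is done, so that sampling takes place on drug. No dose is taken on the day itself. Section 5.1 says off-study procedures should take place "no later than within 36 hours of the last dose of letrozole or placebo".

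**The concern.** The tablet count is an operative instruction to the pharmacies, and it does not deliver the period it is said to cover. The extra month exists so that the 6-month RPFNA, the source of the primary Ki-67 value, is taken while the woman is still on agent. If the supply ends partway through that month, the women who follow the dosing instruction most closely are the ones who run out. The trough serum drawn at the same visit would be affected in the same way.

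The disagreement over supply matters for a second reason. Section 5.7 compares the tablets left over with the number expected to be left over, and that expectation depends on which section a site follows.

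**Working it through.** **Inputs.** 200 tablets (6.9); one a day (5.2); six planned months plus up to one more (6.9, 7.5). Section 7.5 speaks of calendar months. Over all start dates in 2006-2010, 6 calendar months are 181-184 days, 7 are 212-215 and 8 are 242-245.

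**Can the plan's figure be reproduced?** Tablets needed = days x 1.

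| Meaning of 7 months | Tablets needed | Are 200 enough? |
|---|---|---|
| 28-day months, 7 x 28 | 196 | yes |
| 30-day months, 7 x 30 | 210 | no, 10 short |
| calendar months | 212-215 | no, 12-15 short |

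Only a 28-day month makes 200 sufficient, and the protocol defines no such month.

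**What 200 tablets cover.** 200 / 30.44 = 6.57 months. Days left after six months: 200 - 184 = 16 to 200 - 181 = 19, out of an extension of 28-31 days. With the first dose on day 1, the last is on day 200. With no dose on the procedure day, the latest RPFNA on uninterrupted dosing is about day 201.

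**Effect of missed doses.** Gap at the end of the seventh month = (212 to 215) - 200 / adherence.

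| Adherence | 200 / adherence (days) | Gap (days) |
|---|---|---|
| 100% | 200.0 | 12-15 |
| 99% | 202.0 | 10.0-13.0 |
| 98% | 204.1 | 7.9-10.9 |
| 97% | 206.2 | 5.8-8.8 |
| 95% | 210.5 | 1.5-4.5 |

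The gap closes at 200 / 212 = 94.3% to 200 / 215 = 93.0%.

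**Supply stated in section 5.1.** Eight calendar months need 242-245 tablets, which is 42-45 more than section 6.9 dispenses. Leftover tablets for a fully adherent woman seen at exactly six months:
- 200 tablets (6.9): 16-19
- a full seven-month supply (5.2, 5.7): 28-31
- an eight-month supply (5.1): 59-62

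**The case against.** The strongest reply is that very little follows from this. The planned six months are covered with 16-19 days to spare. A shortage needs an RPFNA in the last 12-15 days of an optional extension, adherence above about 93-94%, and no further tablets issued. Women keep track of missed doses (5.2) and coordinators review dosing by telephone each month (7.4), so someone close to her last tablet could be identified and scheduled. The protocol states no resupply before the 6-month visit, but does not forbid one. Section 6.9 also qualifies the extra month as approximate. All of this stands as a limit on the harm. It does not make 200 tablets last seven months, and section 7.5 allows a whole further month without qualification.

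Three stronger readings are tempting and are not supported:

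- **A different blinded treatment length.** A reader might infer from section 5.1 that blinded dosing is seven months rather than six, and that 7 + 6 = 13 months contradicts section 4.3 ("6 months for randomization portion, 12 months if participates in the optional open label period"). But the seven months in 5.1 can be read loosely as six planned plus one for scheduling. Section 4.3 gives the nominal length of participation, in a criterion about continuing hormones, and is not a dosing rule. The clear conflict is the supply: eight months against seven. Even on the loose reading, eight does not fit the open-label period, where six months plus one of overage is seven.
- **A breach of the 36-hour rule for every late RPFNA.** That rule concerns off-study procedures. It does not clearly bind a woman who continues to open label at month 6.
- **Damage to the primary result.** Section 12.2 makes a woman evaluable for efficacy if she has a pre and a post specimen, and its secondary analysis asks for at least three months of medication. Compliance in section 5.7 is tablets taken over days due, which does not depend on the amount dispensed provided that quantities dispensed and returned are recorded as section 6.10 requires.

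**Conclusion.** Minor, but wrong as written. The 200 tablets in section 6.9 last about 6.6 months, not seven: 12-15 tablets short on calendar months and 10 short on 30-day months. They cover the planned six months and 16-19 days of the extension. A woman above about 93-94% adherence with an RPFNA in the last 12-15 days of that extension could be off agent before sampling, by at most 12-15 days. That would defeat the aim in section 7.5 and, if she is going off study, the 36-hour limit in section 5.1. Section 5.1 also conflicts with sections 5.2, 5.7, 6.9 and 7.5 on supply.

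This rests on one tablet a day, calendar months and no resupply before the visit. The protocol does not say how many RPFNAs would fall that late, so the number of women affected cannot be estimated. The effect on the primary comparison is probably negligible.

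**What to change.** Amend section 5.1 to a seven-month supply per period, and reword its blinded duration as six months planned plus up to one for scheduling. Use the same wording in sections 5.2, 5.7, 6.9 and 7.5. Then choose one of the following:

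1. **Keep 200 tablets.** Describe them in section 6.9 as about 6.5 months, change the seven-month wording elsewhere to match, and require the 6-month RPFNA by about day 201. This needs no extra drug. The scheduling window falls from 28-31 days to 16-19, so some RPFNAs may fall outside it.
2. **Dispense at least 215 tablets per period**, in practice three bottles. This keeps the full month. It costs one extra bottle per woman per period: 108 bottles for the randomised period at planned accrual, and up to 108 more if every woman takes open label (uptake is not given). A fully adherent woman seen at exactly six months would return 300 - 184 = 116 to 300 - 181 = 119 tablets.

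Either way, state the tablet count for the open-label period as well; section 6.9 gives one only for entry.

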6.10 Agent Accountability

The Site Principal Investigator, or a responsible party designated by the Site Principal Investigator, must maintain a careful record of the inventory and disposition of all agents using a Drug Accountability Record Form (DARF). The Site Principal Investigator is required to maintain adequate records of receipt, dispensing and final disposition of study agent. This responsibility has been delegated to the Investigational Pharmacy at each participating site. Include on receipt record from whom the agent was received and to whom study agent was shipped, date, quantity and batch or lot number. On dispensing record, note quantities and dates study agent was dispensed to and returned by each participant.

6.11 Packaging and Labels

Letrozole and letrozole placebo will be supplied by Novartis in a form ready for dispensing. Each bottle will be labeled with a one-part label identifying study specific information, such as Study title, HSC protocol number, dosing instructions, recommended storage conditions, the name and address of the distributor, randomization number, and a caution statement indicating that the agent is limited by United States law to investigational use only and the agent should be kept out of reach of children.

6.12 Storage

Storage should be in a locked cabinet with limited access, at room temperature.

6.13 Registration/Randomization/Consent

Potential subjects will be registered for the screening portion of the study by site study coordinator and principal investigator on a site screening log. Potential subjects will be given a unique screening number by the site staff and this will be affixed to all eligibility specimens and documents that will be sent to KUMC for review. No PHI should be attached to these items.

Site staff will not randomize a subject until verification by KUMC Trial Coordinator by means of a faxed request (standard form provided for this purpose which will include an eligibility checklist and notification of acceptable consent) for a particular potential subject. The designated KUMC Trial Coordinator will fax back to the Site Coordinator an approval to randomize the subject based on the review of the eligibility checklist provided by the site.

Approved eligible subjects will be randomized by a randomization schedule at each site, prepared and provided by the Study Statistician. The site staff and subjects will be blinded as to the assignment to drug or matched placebo.

The subject will be assigned a randomization number, after stratification by site and type of hormone replacement therapy. The randomization schedule will be stratified by site (each site will be provided a unique list for use only at that site), and whether the subject is on an estrogen preparation alone, or estrogen plus a progestin preparation. Randomization will be in sequential order according to the randomization list provided. Subjects approved for randomization will be assigned a site specific randomization number, consisting of four digits. The first digit will identify the site (to be determined later) and three digits identifying the specific potential subject.

Sub-contracted sites other than KUMC may use the study consent for the screening RPFNA, or use a research/clinical consent for that purposes. Subjects are not officially on study until they have made it through the entire eligibility process. KUMC will use the High Risk Protocol Consent (KUMC HSC#4601) for the purposes of the screening RPFNA.

